1.3.3 Subject recruitment and allocation

All recruitment, consenting, screening, and enrollment questions will be asked by trained study staff in a private room.

Recruitment:

We will be recruiting until a total of 133 women are randomized. The proposed research will take place at Atlanta Women's Center (AWC). Women who attend the AWC for an abortion will be approached during their preoperative evaluation. The flow of steps to assess women presenting for abortion occur in the following order: ultrasound for gestational age, blood draw to assess hemoglobin and Rh factor, options counseling to determine whether surgical abortion is chosen, financial payment, and nurse preoperative review. Trained research staff will approach these women to determine interest in participating in the study, consent those interested in participating, and then participants will be screened for eligibility. A standard recruitment script will be employed (Appendix A). We will enroll participants after financial counseling and before nurse preoperative review. Consent will be obtained at time of enrollment.

Screening and consent:

Individuals who are interested in participating will review the informed consent and eligibility screening. We will screen for eligibility using an eligibility checklist (Appendix A). Patient contact information will be collected at this time. Enrollment will occur after financial counseling, and consent will be obtained at time of enrollment. Following enrollment, the patient's medical history will be reviewed by a clinician to ensure study eligibility. Randomization will occur and intervention will be received after enrollment. The study drug (intervention or placebo) will be dispensed by the PI, Clinic Director, or Clinic Staff Nurse. Both the Clinic Director and Clinic Staff Nurse are registered nurses with required CITI training.

Potential subjects will typically do their 24hr consent over the phone prior to presenting to the clinic. Thus, the preoperative evaluation and procedure both occur on the same day. We are not approaching any potential subjects for interest in the study until after they have selected local anesthesia and paid for their procedure.

The abortion providers are not involved in the discussion with the patient regarding “timing, method, or procedures used to terminate a pregnancy”. This is a discussion that the clinic staff has with the patient after ultrasound evaluation (to confirm gestational age) and financial counseling. The patient also goes through options counseling with clinic staff (not the abortion provider) during which the different types of procedures are discussed (medical vs surgical procedure based on gestational age). The study team will only begin interaction with the potential subject/patient once they’ve selected local anesthesia and paid for their procedure. The Investigators will only be involved after this point. Investigator involvement may include consenting the subject, administering the study drug, performing the procedure, and other study related activities such as administering the questionnaire. There is one abortion provider per day at Atlanta Women’s Clinic and if an investigator is the provider for that day, she will not participate in any other study-related activities.

The person obtaining the consent will be a member of the study team. This person will have no prior contact with the study patient. This person will not be scheduling the appointment, discussing options counseling, advising about the procedural options, or performing ultrasound or other laboratory work-up for the participant prior to the procedure. There is a clear separation between study staff and clinic staff prior to the enrollment of participants into the study,

Randomization, Allocation Method and Blinding:

Women who enroll and meet study inclusion criteria will be eligible for participation. *Randomization* will be done using computer-generated random numbers (randomization.com) in variable blocks of 4 and 6. *Allocation* concealment will be maintained by identically labeled sealed sequentially numbered opaque pill containers. Gabapentin and placebo tablets will be indistinguishable by appearance (both gelatin capsules), thus maintaining blinding for participants and assessors. To maintain double *blinding* for both investigators and participants, an individual not associated with study conduct will create the randomization sequence and allocation containers. The study drug

and placebo will be obtained through the Duke Investigational Drug Service that will vacuum seal the containers prior to shipping to the clinic. The randomization assignments will only be revealed at the point of data analysis or if an interim assessment is needed.

1.3.4 Description of the drugs and devices to be studied

Gabapentin was originally approved by the U.S. Food and Drug Administration (FDA) in December 1993, for use as an adjuvant (effective when added to other antiseizure drugs) medication to control partial seizures in adults; that indication was extended to children in 2000 [21], and later approved for treating postherpetic neuralgia. In December 2004, the FDA granted final approval to a generic equivalent to Neurontin made by the Israeli firm Teva. It was originally synthesized to mimic the chemical structure of the neurotransmitter GABA. The mode of action of gabapentin is believed to be through its binding to the alpha 2 delta subunit of the DRN voltage-dependent calcium channels. This causes decreased entry of calcium into the nerve endings, resulting in decreased release of nociceptive neurotransmitter (glutamate, substance p, noradrenaline). Other proposed mechanisms of action include the binding to NMDA receptors, sodium channel receptors, monoaminergic receptors, and opioid receptors.

Overall, gabapentin is a safe drug. The most common side effects of its use include: dizziness, somnolence, fatigue, ataxia, peripheral edema, nystagmus, nausea and vomiting, asthenia, headache, weight gain, and amblyopia. Most of the side effects are associated with chronic usage. Other extremely rare side effects include: DRESS (drug reaction with eosinophilia and systemic symptoms), multi-organ hypersensitivity, withdrawal seizures (if given for epilepsy), suicidal behavior and ideation, neuropsychiatric reactions in pediatric patients (3-12 years of age), and sudden death.

Drug Interactions are rare and mild. Maalox or other aluminum or magnesium hydroxides decreases bioavailability of gabapentin by 20% if given at same time. Additionally, when used with hydrocodone or morphine, gabapentin may decrease the AUC. Abuse and withdrawal potential is low. The drug is almost entirely metabolized through renal metabolism, where it is eliminated unchanged in the urine, thus dosage adjustments are needed for patients with renal impairment. The half-life for the medication is 5-7 hours with a 2 hour time to peak plasma concentration.

1.3.5 Admission procedure

After financial clearance, all participants who have opted for a surgical abortion with local anesthesia will be approached for interest in the study. A study interest card will be placed on their medical chart, and the participant will be accompanied by the financial counselor and taken to the designated research room. This designated research room is a private room located in AWC. The study team will then review the recruitment script with the patient. If the patient is interested in the study, then a member of the study team will consent the participant. Following consent and enrollment into the study, the participant will be taken to the clinical nurse. The nurse will review the participant's chart to ensure eligibility for surgical abortion and gabapentin administration. The participant will then receive the study drug or placebo. Following administration of the drug, the participant will return to the designated research room. The study staff will review the baseline questionnaire that includes demographic questions. Following completion of the questionnaire, the participant will continue to wait in the designated research room or preoperative area. One hour after the administration of the drug or placebo, the participant's chart will be placed back into rotation for surgical procedures. The study team will accompany the participant to the clinical lounge where they will gown and prepare for the procedure. The participant will then undergo the procedure in order of chart placement. Prior to initiating the abortion procedure, study staff will administer the preoperative questions. Staff will administer the intraoperative questions at the time of evacuation during the uterine aspiration, and at time of removal of the speculum at the end of the procedure. Immediately following the procedure, the study staff will follow the participant to the recovery room to complete the remaining questions assessed at 10 minutes, 30 minutes and at discharge. Per clinic protocol, patients remain in the recovery room for approximately 30-60 minutes after surgical abortion with local anesthesia. When the discharge questions are complete, the participant will receive a \$30 gift card and be reminded to expect a follow-up call the following day (post operative day #1).

1.3.6 Follow-up procedure

On the day following the procedure (approximately 24 hours after the abortion), study staff will contact the participant to complete the follow-up questions. The participant will be contacted via email, text communication and telephone. Upon completion of the questions, an additional \$20 will be added to the original gift card.

Withdrawals, losses, and deviations:

Randomization to the study method will occur after completion of all intake forms and consent, immediately before the pill is to be taken, thus reducing the possibility of withdrawal after randomization. Any significant medical history will be reviewed prior to enrollment with a clinician at the clinic to ensure study eligibility. Primary outcome measures and most secondary outcome measures will be assessed immediately before, during or after the abortion procedure, thus any loss to follow-up will be limited to those who consent to, but change their mind while waiting for their procedure. Based on current clinical practice at this clinic, withdrawal after consent is extremely rare. Our secondary outcomes assessed post-operatively after discharge will be collected via telephone. We will maximize completion of these assessments through the following steps: participants will be told beforehand about the telephone contact following the procedure, a cellular telephone number will be collected and tested at the clinic, a secondary phone number and email will be collected as a backup, participants will be given a contact number for the study coordinator should they have any challenges with receiving phone calls, and participants will receive an additional \$20 sent to their gift-card following the completion of their phone assessment. Subjects will be considered lost-to-follow-up if they have not responded to the follow up survey within 48 hours after their procedure. As we anticipate some loss to follow-up for our secondary outcome on post-operative day 1, we have adjusted our study enrollment to provide some accommodation for 20% loss to follow-up.

1.3.7 Criteria for discontinuation

An adverse event (AE) is defined as any health-related reaction, effect, toxicity or abnormal laboratory result that a study participant experiences during the course of the study, irrespective of relationship to the study intervention. This includes changes in a participant's condition that have or could have a deleterious effect on a participant's health

or well-being. A serious adverse event (SAE) is defined as any experience that is fatal or life threatening, requires in-patient hospitalization or prolongation of an existing hospitalization, or results in a persistent or significant disability or incapacity.

This study uses an additional medication for pain control in the setting of outpatient abortion. These activities are not anticipated to be associated with any deleterious impact on participants' health or well-being beyond the risks associated with the abortion procedure. AEs will be managed according to good clinical practice and the judgment of the on-site physician. All clinical and laboratory AEs will be followed-up closely by study staff. Any SAEs will be expeditiously reported to the principal investigators, via a designated SAE form. Notification and submission of SAE forms should occur within 48 hours of the site awareness of the SAE. The PI will then make the final independent judgment as to the severity, relatedness, and anticipated or unanticipated nature of the SAE and finalize the Human Subjects Adverse Event Report Form. If the event is determined to be serious, unanticipated, and the relationship is anything other than probably or definitely not related, then the PI will report the event within 48 hours and submit the required forms to the IRB at Emory. Thus, all anticipated SAEs that are at least possibly related to study intervention and all deaths that are at least possibly related to study intervention will be submitted to Emory IRB.

The study may be discontinued at any time by IRB at a participating institution or the Office for Human Research Protection. One of the co-investigators (TH) will review any adverse event and periodically review side effects to see if there are an increased number of events than anticipated by routine clinical care. If any suspicion for increased risk exists, study allocation may be revealed for a preliminary analysis and if related to the study intervention, the study could be prematurely ended.

Data Monitoring Committee/Study Termination:

A Data Monitoring Committee (DMC) will be created to perform regular and timely review of data in order to identify early, significant benefit or harm for patients while the trial is in progress. On a regular basis (frequency as to be determined by the DMC based on the enrollment rate and potential risk to subjects), non-identified safety data will be

communicated to the DMC who will then meet to review the data. The DMC will be composed of three faculty members within the Emory University Department of Gynecology and Obstetrics. Individuals who are investigators or co-investigators cannot be members. No member of the research study team will be on the committee. Members must have no financial, scientific, or other conflicts of interest with the study. All investigators understand that the DMC serves as additional human subject's protection, but does not supplant reporting of significant adverse events to the Emory IRB. The DMC may devise its own stopping rules, and if there are significant numbers of adverse events, the DMC will recommend continuation, modification, or termination of the study after each meeting. This recommendation will be communicated to the principal investigator who is responsible for reviewing the recommendation and forwarding it to the IRB. .

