1.3 Design and Methodology

1.3.1 Research design and General Methodology Approach

This is a randomized double-blind placebo-controlled trial evaluating the impact of gabapentin given preoperatively on perioperative pain scores for women receiving a surgical abortion. Randomization will be done using computer generated random Fellowship in Family Planning Research Proposal Outline

numbers. Allocation concealment will be maintained by identically labeled sealed sequentially numbered pill containers. Gabapentin and placebo will be packaged in identical gelatin capsules and sealed by an independent pharmacy. Gabapentin and placebo gelatin capsules will be indistinguishable by appearance, thus maintaining double blinding.

Primary study outcomes: Our primary outcome measure will be pain score using a 100-mm visual analog scale (VAS) measured intraoperatively at time of evacuation.

Secondary outcomes: We will also be measuring pain on the 100-mm VAS preoperatively immediately prior to the procedure, at completion of the procedure (removal of the speculum), 10 minutes and 30 minutes following the procedure, and at discharge. Nausea and vomiting will be assessed during the same time intervals using a 100-mm VAS scale. Anxiety prior to the procedure will be measured using the preoperative state trait anxiety inventory. Side effects will be assessed using a checklist prior to discharge. We will also be contacting participants on post-operative day 1 to assess pain, nausea, vomiting, side effects and general satisfaction with the procedure (on a 5-point scale). The quantity and type of medications used perioperatively and post-operatively, including medications used at home in the 24 hours post-operatively, will be abstracted from the clinical record and assessed on the phone. Outcome measures will be collected on a tablet using a web-based password-protected relational database (REDCap). All VAS scale scoring and questionnaires will be completed using this database on a research-designated tablet.

Baseline Characteristics and Covariates:

We will collect baseline demographics, medical history (gravidity, parity, prior abortions (medical and surgical), gestational age, drug and alcohol use, psychiatric or sexual assault history, medications used at home and given at the clinic preoperatively, and indication for procedure (personal/social, fetal, or maternal health). This information will also be obtained using a research-designated tablet.

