Gabapentin is indicated for the management of postherpetic neuralgia in adults, as adjunctive therapy in the treatment of seizure disorder, and for chronic pain management. Gabapentin is contraindicated in patients who have demonstrated hypersensitivity to the drug or its ingredients. When gabapentin is taken for chronic use, side effects are noted. Drug reaction with eosinophilia and systemic symptoms, also known as multiorgan hypersensitivity, has occurred with gabapentin. These reactions can be fatal or life threatening. Typical symptoms include but are not limited to fever, rash, lymphadenopathy, hepatitis, nephritis, hematological abnormalities, myocarditis, or myositis. In the presence of signs or symptoms, prompt evaluation and discontinuation of gabapentin is warranted. Although rare, gabapentin can cause anaphylaxis and angioedema after the first dose or any time during treatment. The patient should be instructed to discontinue the medication and seek immediate medical attention.

During the controlled epilepsy trials in patients older than 12 years of age, the patients who received gabapentin (up to 1800mg daily) reported greater rates of somnolence (19%), dizziness (7%) and ataxia (6%) when compared to the placebo group. During the controlled trials in patients with postherpetic neuralgia taking doses of gabapentin up to 3600mg, patients reported increased somnolence (21% of the gabapentin arm vs. 5% of the placebo arm), and dizziness (28% of the gabapentin arm vs. 8% of the placebo arm). Patients should be carefully observed for signs of central nervous system depression, especially when gabapentin is used with other drugs with sedative properties.

Antiepileptic drugs (AEDs), including gabapentin, increase the risk of suicidal thoughts or behavior in patients taking these drugs for any indication. Patients should be monitored for the emergence or worsening depression, suicidal thoughts or behavior, and/or unusual changes in mood or behavior. Pooled analysis showed that patient randomized to one of the AEDs had approximately twice the risk of suicidal thinking or behavior compared to patients randomized to placebo. It should be noted that these trials had a median treatment duration of 12 weeks.

During the premarketing development of gabapentin, there were 8 sudden or unexplained deaths that were recorded among a cohort of 2203 epilepsy patients treated

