with gabapentin. This rate exceeds that expected in a healthy population that is matched for age and sex. This rate falls within the range of estimates for the incidence of sudden unexplained deaths in patients with epilepsy not receiving gabapentin.

Below is a table that outlines adverse reactions that occurred in at least 1% of gabapentin treated patients with postherpetic neuralgia participating in placebo-controlled trials.

Adverse reactions in Pooled Placebo-Controlled Trials in Postherpetic Neuralgia		
	Gabapentin (N=336, %)	Placebo (N=227, %)
Body as a whole		
Asthenia	6	5
Infection	5	4
Accidental injury	3	1
Digestive system		
Diarrhea	6	3
Dry mouth	5	1
Constipation	4	2
Nausea	4	3
Vomiting	3	2
Metabolic and nutritional disorders		
Peripheral edema	8	2
Weight gain	2	0
Hyperglycemia	1	0
Nervous system		
Dizziness	28	8
Somnolence	21	5
Ataxia	3	0
Abnormal thinking	3	0
Abnormal gait	2	0
Incoordination	2	0
Respiratory		
Pharyngitis	1	0
Special senses		
Amblyopia	3	1
Conjunctivitis	1	0
Diplopia	1	0

Otitis media

1

0

Below is a table that outlines adverse reactions that occurred in at least 1% of gabapentin-treated patients over the age of 12 who participated in placebo-controlled trials on epilepsy.

Adverse reactions in Pooled Placebo-Controlled Trials in Epilepsy patients over age 12

Gabapentin (N=543, %)

Placebo (N=378, %)

Body as a whole

Fatigue	11	5
Increased weight	3	2
Back pain	2	1
Peripheral edema	2	1

Cardiovascular

Vasodilation 1 0

Digestive system

Dyspepsia	2	1
Dry mouth and throat	2	1
Constipation	2	1
Dental abnormalities	2	0

Nervous system

Dizziness	17	7
Somnolence	19	9
Nystagmus	8	4
Ataxia	13	6
Tremor	7	3
Dysarthria	2	1
Amnesia	2	0
Depression	2	1
Abnormal thinking	2	1
Abnormal coordination	1	0

Respiratory

Pharyngitis	1	0
Coughing	2	1

Skin and appendages

Abrasions 1 0

Urogenital system

Impotence 2 1

Special senses

Amblyopia	4	1
Diplopia	6	2

Data presented here is directly from FDA prescribing information. The gabapentin drug information in this section is from the FDA website. Our study will only administer a one-time dose of gabapentin, and therefore we do not anticipate the side effects listed that are more likely associated with chronic use.

Reference:

<http://www.drugs.com/pro/gabapentin.html#S5.4>

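### The side-effect review in section 1.3.7 uses routine care as its benchmark and can lead to allocation being revealed without passing through the DMC

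*Combined protocol and SAP*

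**What the plan says.** Section 1.3.7 (Criteria for discontinuation) has one co-investigator review adverse events and "periodically review side effects to see if there are an increased number of events than anticipated by routine clinical care". It continues: "If any suspicion for increased risk exists, study allocation may be revealed for a preliminary analysis". Where the excess is then attributed to gabapentin, an early end to the trial is possible. The section gives no rate, count or list of expected drug effects, and does not say who would see the allocation or run the analysis.

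Under its Data Monitoring Committee heading, the same section creates a DMC of three faculty members, none of them investigators or study team members. The DMC receives non-identified safety data and may set its own stopping rules. The co-investigator's review is not linked to it.

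Section 1.3.3 intends participants, assessors and investigators to be blinded, and has a person not associated with study conduct create the sequence and the containers. It allows investigators to administer the questionnaire, except on a day when they are the abortion provider. It lets assignments be revealed at data analysis or if an interim assessment is needed, and does not define that assessment.

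On side effects, section 1.3.1 states "Side effects will be assessed using a checklist prior to discharge", and section 1.3.4 states "The most common side effects of its use include: dizziness, somnolence, fatigue, ataxia". Section 2 (Gabapentin) gives rates from trials in epilepsy and postherpetic neuralgia. It adds that, with one dose only, the study does not anticipate the listed effects that are more likely tied to chronic use.

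**The concern.** The comparator does not match the question. While the trial is blinded, the counts pool both arms, so about half the women counted have had gabapentin (assuming 1:1 allocation; no ratio is stated). Routine care has no gabapentin. A genuine excess of dizziness or somnolence would count against the benchmark even though the protocol already lists both. The checklist may also record more symptoms than routine care does. The relatedness condition does not separate new harm from known effects, because a known drug effect is related to the intervention. The concurrent placebo arm is the natural comparator, but it comes in only once allocation has been revealed.

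Two things are at stake. One is the blind: nothing limits the reveal to women already treated, or keeps it from people who may also be asking participants for their pain scores. The other is the trial's completion: an early end for an effect already expected could leave the pain question underpowered.

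**Working it through.** **1. Inputs.** From the tables in section 2 (Gabapentin), dizziness on gabapentin against placebo is 28% vs 8% in postherpetic neuralgia and 17% vs 7% in epilepsy. From section 1.3.11: difference 15 mm, SD 26 mm, 96 women for 80% power, 133 enrolled.

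Assumed, because the documents do not give them: 1:1 allocation; a review at 66 women (33 per arm, about half of 133); a routine-care rate equal to the quoted placebo rate; and a single dose producing a fraction f of the repeated-dosing excess.

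**2. The plan's own figure.** A two-sided 5% t-test with 48 per arm, 15 mm and SD 26 mm has power 0.799, so 96 women for 80% is reproduced.

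**3. Pooled count.** Count = Bin(33, placebo rate + f × excess) + Bin(33, placebo rate). The benchmark expectation is 66 × placebo rate: 66 × 0.08 = 5.3 (neuralgia) and 66 × 0.07 = 4.6 (epilepsy). At f = 1 the expected count is 33 × 0.28 + 33 × 0.08 = 11.9 and 33 × 0.17 + 33 × 0.07 = 7.9.

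**4. Chance of an apparent excess.** Two readings of an increased number are shown: any count above the benchmark expectation, and a count at or above the exact one-sided 5% limit (10 for neuralgia rates, 9 for epilepsy rates). The protocol specifies neither.

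| Share of excess, f | Expected count (neuralgia / epilepsy) | Above expectation | Flagged by 5% limit |
|---|---|---|---|
| 1 | 11.9 / 7.9 | 99% / 91% | 78% / 40% |
| 0.5 | 8.6 / 6.3 | 88% / 76% | 35% / 17% |
| 0.25 | 6.9 / 5.4 | 71% / 64% | 15% / 9% |
| 0 | 5.3 / 4.6 | 44% / 50% | 4% / 4% |

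The above-expectation column is close to a coin toss with no drug effect at all, so its high values should not be read as false-alarm rates. The 5% column is the fairer guide.

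**5. Sensitivity to the routine-care rate.** If routine dizziness were 20%, the 5% limit (20 events) would flag 53%, 19% or 9% for a drug excess of 20, 10 or 5 points.

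**6. If the trial ended at 66 women.** Power for 15 mm (SD 26 mm) would be 64%, against 80% at 96 and 91% at 133. The documents allow no estimate of how likely such an ending is.

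**7. Text against table (separate point).** Section 2 says of epilepsy patients: "who received gabapentin (up to 1800mg daily) reported greater rates of somnolence (19%), dizziness (7%) and ataxia (6%) when compared to the placebo group". The table headed "Adverse reactions in Pooled Placebo-Controlled Trials in Epilepsy patients over age 12" gives somnolence 19 vs 9, dizziness 17 vs 7 and ataxia 13 vs 6. The text's 7% and 6% are the placebo-column values. The somnolence figure agrees with this table, and the neuralgia figures in the text agree with theirs.

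**The case against.** The only rates in the documents come from repeated dosing, up to 1800 mg daily or up to 3600 mg, in other patient groups. Sections 1.3.4 and 2 say that most side effects go with chronic use. The condition is a reviewer's suspicion, not a count crossing a line. Allocation may be revealed and the study could be ended, the latter only if the excess is related to the intervention. The reveal is itself for a preliminary analysis, presumably between arms, so the placebo arm would inform any decision to stop. The DMC sits in the same section and reviews safety regularly.

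Much of this stands. A reader might infer that known gabapentin effects would, or probably will, meet the condition. The documents do not support that: with a quarter to half of the listed excess, the 5% limit flags only 9% to 35% of the time. A reader might also infer that the study team will be unblinded, but section 1.3.7 is silent on who sees the allocation. Nor would pain scores be badly biased if only past assignments were revealed. With blocks of 4 and 6, at most 3 later assignments become certain; with an assumed 5 to 10 mm effect of knowing, that is 3/66.5 × 5 to 10 = 0.2 to 0.5 mm. No inflation of type I error follows from the plan as written.

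What the objection leaves unanswered is that the benchmark excludes the study drug, no expected effects are listed for the review, the route is not linked to the DMC, and the extent and audience of a reveal are left open.

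**Conclusion.** The point holds as a weakness in the monitoring rule, not as a forecast that the trial will be unblinded or stopped. A listed drug effect could appear as an excess over routine care, and the plan then permits a reveal with no stated recipient, no DMC step and no protection for unused assignments or outcome collectors.

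The size is uncertain: on the 5% limit, from 4% with no single-dose excess to 78% with the full neuralgia excess. This rests on a review at 66 women, 1:1 allocation and placebo rates standing in for routine care. Every later step stays discretionary. The change is worth making because it is cheap and uses a committee the protocol already has.

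The epilepsy mismatch is real but minor. It affects two figures, and section 1.3.7 does not use them. It should not be read as a general misstatement of gabapentin's effects.

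**What to change.** In section 1.3.7, replace the routine-care comparison and the sentence on revealing allocation with wording to this effect: *The co-investigator reviews blinded data only. Any concern goes to the DMC, which compares side effects between gabapentin and placebo participants already treated, against a list of expected effects that it has recorded beforehand. A person outside study conduct prepares the comparison, and only the DMC sees it. Unused assignments stay sealed and outcome collectors stay blinded. Unblinding of an individual for safety is not affected.*

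In section 1.3.3, point the interim assessment to this rule.

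Separately, reconcile the epilepsy dizziness (7%) and ataxia (6%) figures in the text of section 2 with the table (17 vs 7 and 13 vs 6).

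The cost is protocol wording and some time from an independent person for each comparison. Section 1.3.10 plans a statistician only as needed, so one may have to be named. No extra participants are needed, and SAE reporting is unchanged. The downside is one added step before any group-level unblinding.

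### Does leaving open who may see a mid-trial allocation reveal put the double blind at risk?

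*Combined protocol and SAP*

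**What the plan says.** Section 1.3.3, under randomization and blinding, sets the general rule: "The randomization assignments will only be revealed at the point of data analysis or if an interim assessment is needed". The same section says that blinding covers participants, assessors and investigators, and that someone outside study conduct creates the sequence and the numbered containers.

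Section 1.3.7 has a co-investigator who "will review any adverse event and periodically review side effects". It then adds: "If any suspicion for increased risk exists, study allocation may be revealed for a preliminary analysis". If the signal is related to the intervention, the study could end early.

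The DMC paragraph of 1.3.7 sets up a separate body of three faculty members. On membership it says "Individuals who are investigators or co-investigators cannot be members". On output, "the DMC will recommend continuation, modification, or termination of the study after each meeting", and "This recommendation will be communicated to the principal investigator". It does not mention the co-investigator's reveal, and the reveal sentence does not mention the DMC.

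On who meets participants, section 1.3.3 says "The study drug (intervention or placebo) will be dispensed by the PI, Clinic Director, or Clinic Staff Nurse". It also lets investigators take part in "other study related activities such as administering the questionnaire".

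On reporting, 1.3.7 first sends serious, unanticipated events that are not judged unrelated to the IRB within 48 hours. The next sentence is framed as a consequence, but it names anticipated SAEs that are possibly related, plus possibly related deaths, and it gives no time limit.

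**The concern.** The trial is double-blind, at one site, with a subjective primary outcome recorded while study staff are beside the woman. The reveal sentence is in the passive voice and names no recipient. The review that precedes it belongs to a co-investigator, who is among those meant to stay blinded and who cannot sit on the DMC. The PI may dispense study drug, and investigators may put the questionnaire to participants. Read literally, nothing in these sections keeps revealed codes away from someone who still doses or questions later women. Because containers are sequentially numbered, a full list would identify every remaining assignment. If that knowledge changed how pain was asked about or recorded, the arm difference would be biased from then on and the nominal 5% error rate would no longer hold.

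The IRB sentences raise a smaller worry: the second does not follow from the first, so staff might be unsure which events go to the IRB and by when.

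**Working it through.** The plan gives no figure on this point, so the check sizes the possible bias under stated assumptions.

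**Inputs from the plan (1.3.11 and 1.3.3):** SD 26 mm; 133 women; variable blocks of 4 and 6.

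**Assumptions, not in the plan:** the reveal comes after 67 women, leaving 133 − 67 = 66 exposed; knowing the allocation shifts the arm difference by d = 2.5 or 5 mm per exposed woman; block sizes 4 and 6 are equally likely and unknown to the guesser, who guesses optimally.

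**Formulas**

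- Standard error of the arm difference: 26 × 2 / √133 = 4.51 mm.
- Net information per container: 2 × (accuracy of guess) − 1.
- Overall shift: d × (net information × exposed women) / 133.
- False-positive rate: two-sided rejection at 1.96 when the standardised difference is centred at shift / 4.51.

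**What each kind of reveal gives away**

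- (a) Past codes seen once. Simulated accuracies for the next six containers are 0.791, 0.600, 0.583, 0.520, 0.519 and 0.500. The excess over one half is 0.291 + 0.100 + 0.083 + 0.020 + 0.019 + 0 = 0.51 extra correct guesses in total. With the reveal at a random point between containers 20 and 120 it is 0.37.
- (b) Past codes seen repeatedly from then on. Accuracy is 0.692, so net information is 2 × 0.692 − 1 = 0.384.
- (c) Full list released. Net information is 1 for all 66 women.

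| Reveal | Net information × exposed | Shift at 2.5 / 5 mm | Rate at 2.5 / 5 mm |
|---|---|---|---|
| (a) | 2 × 0.51 = 1.02 | 0.02 / 0.04 mm | 5.0% / 5.0% |
| (b) | 0.384 × 66 = 25.3 | 0.48 / 0.95 mm | 5.1% / 5.5% |
| (c) | 1 × 66 = 66 | 1.24 / 2.48 mm | 5.9% / 8.5% |

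For (c) at 5 mm: 5 × 66 / 133 = 2.48 mm, and 2.48 / 4.51 = 0.55 standard errors, which gives 8.5%. A simulation with permuted blocks and a t-test (20,000 trials) gave 8.4%, against 4.8% with no bias. The rate for (c) at 5 mm is 11.5% if the list is released after 44 women and 6.6% if after 89.

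**Which row applies.** Section 1.3.7 describes a preliminary analysis of whether events are related to the intervention. That analysis can use only women who have taken a capsule, so row (a) is closest to the text. Even at an assumed d = 10 mm, row (a) gives 10 × 1.02 / 133 = 0.08 mm.

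**All rates are conditional on a reveal.** If, as an assumption, one trial in ten had a reveal of type (c) at 5 mm, the average rate would be 0.90 × 5.0% + 0.10 × 8.5% = 5.35%.

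**IRB sentences side by side.** The first covers unanticipated related SAEs. The second covers anticipated related SAEs and related deaths. Together they cover every SAE that is at least possibly related. Separately, 1.3.7 already requires any SAE to reach the principal investigators within 48 hours of site awareness. Only the onward step to the IRB under the second sentence has no stated time.

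**The case for a change.** The best argument for a change is that the gap is real and cheap to close. The person placed to prompt a reveal belongs to the group that must stay blind, the plan already has an independent DMC that could receive the result, and the possible rate runs from 5.0% to 11.5% according to something one sentence could settle. Identical capsules do not protect the blind from anyone who has seen the list. The rule that an investigator acting as the day's provider does no other study work does not cover an investigator who is not operating that day.

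What stands is the silence: these sections name no recipient and make no link to the DMC. The consequence does not stand. The top of the range needs codes for undispensed containers, which a safety analysis does not use and no section offers. Section 1.6 assigns consent and data collection to dedicated study staff, and 1.3.5 has study staff ask the outcome questions. The Clinic Director and Clinic Staff Nurse dispense drug but are given no outcome role. The participant stays blinded, and it is her own pain that is rated. If harm were confirmed the study could end early, leaving few or no exposed women.

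A rule sending by-arm results to the DMC alone would not be a clear gain either. It would shut out the IRB, which 1.3.7 allows to discontinue the study at any time. It would also add a step to a safety review when the frequency of DMC meetings is still to be set.

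On the IRB sentences, the objection stands as a matter of wording: the second does not follow from the first, and the documents do not show whether one word is a slip.

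**Conclusion.** No change to the plan is called for. The reveal provision leaves a detail unwritten that those preparing a safety comparison would fill sensibly: they would use the arms of women already dosed and leave the rest of the list closed. On that reading the shift in the primary comparison is under 0.1 mm and the false-positive rate is 5.0%. Reaching 8.5% or more requires a reveal to happen, the release of undispensed codes, and an assumed bias of 5 mm in every exposed woman; none of these comes from the plan. The general rule, that assignments stay closed and that investigators, assessors and participants are blinded, is already stated.

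The two IRB sentences in 1.3.7 are inconsistent as drafted and can be reconciled as an editorial matter. No class of related SAE is lost and no trial result changes.

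This rests on the per-woman bias being an assumption and on the reveal serving a safety question. The DMC paragraph mentions early benefit but specifies no efficacy test. The section between 1.3.13 and 1.5 was not available to this review, so any roles set out there could not be checked.
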